## 16.2 Transcription and analysis of data

The data will be collected using Microsoft Teams video/audio call within Glasgow Caledonian University Teams account. The interview will be recorded and transcription is automatically generated. This is then checked for accuracy and any typos corrected. Audio files will then be deleted. A realist approach to Thematic Analysis (TA) will be adopted in order to develop three types of themes ().

The stages of Braun and Clarke TA will be followed using familiarisation, generating codes, constructing themes, reviewing themes and producing the findings. Using a realist approach will identify the contexts and mechanisms required to produce the desired outcomes. This is particularly important in a large trial being delivered in several organisations and geographical locations. This will enable better understanding of how the intervention worked (or not) in order to assist with translation of sexual health promotion into routine care (28).

## 17. Economic Evaluation

An economic evaluation will be undertaken to determine the cost-effectiveness of the moreRESPECT sexual health promotion intervention. The analysis will be conducted from the perspective of the NHS and personal social services and will assess the relative cost-effectiveness of moreRESPECT compared with usual care. We will measure relevant costs and calculate quality adjusted life years (QALYs) to estimate the incremental cost-effectiveness ratio. We will record the costs of delivering the intervention, including training costs. A bespoke resource use questionnaire was developed during the RESPECT feasibility trial (19). This has been adapted for the present trial based on lessons learnt during the feasibility study and will collect health care usage.

The intention-to-treat population will be used for all analyses and the time horizon will be one year as per the duration of follow-up. Costs and outcome data for the economic analysis will be collected prospectively during the trial using questionnaires following the same timeline as the clinical outcomes, specifically, baseline, 3, 6 and 12 months.

moreRESPECT\_Protocol

IRAS ID: 309345

REC Reference: 23/NW/0157

# 18. Statistical Analysis

A detailed statistical analysis plan will be developed prior to completion of data collection and agreed with the DMC and TSC. All analyses will be undertaken on an intention to treat basis, where participants are analysed as randomised, regardless of whether they complied to their allocation or not. The analyses will be conducted at a 5% significance level using two-sided statistical tests, unless otherwise specified. The flow of participants through the trial will be detailed using a CONSORT flow diagram (). Baseline and outcome data will be summarised descriptively, overall and by arm, with continuous measures using means and standard deviation, and categorical variables by counts and percentages. All assumptions related to the analyses detailed below will be checked.

#### 18.1 Primary analysis

A zero-inflated Poisson regression model will be used to compare the number of unprotected acts between the two groups. The model will be adjusted for relevant baseline covariates as well as site as a random effect. The length of follow-up will be accounted for in the model. Should model assumptions not be met, or there is evidence of overdispersion, other appropriate models will be considered, such as a negative binomial regression model. The incidence rate ratio will be extracted as the point estimate of treatment effect and reported with the 95% confidence interval and p-value.

A compiler average causal effect analysis may be undertaken as a sensitivity analysis of the primary outcome, to account for non-compliance with the intervention.

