telephone call, the University of York's secure Drop-off system or via providing access to the secure Trial Management System. The intervention coordinator/lead will assign an interventionist to the participant and will confirm to YTU who this is; YTU can then add this information to the participants details. The interventionist will keep a record of intervention appointments and attendance by ID number. This will be stored securely until the intervention is completed, and then it will be transferred to the YTU.

The MR researchers who will be collecting follow-up data will be blinded to the participants' allocation. Participants will be asked not to reveal if they had the intervention or not and any accidental revelation of the trial arm will be recorded by the MR researcher as unblinded. Those who deliver the intervention will know the allocation but will not communicate this to the MR researchers working on the study. The trial statisticians and the health economist will not be blinded to allocation.

The participants GP and NHS Care Provider will be informed about their patients' study participation via letter generated from the trial management system; however, they will not be informed about allocation status, reducing the risk of inducing behaviour change based on this knowledge. However, allocation may be revealed to a participant's GP and NHS Care Provider in response to an adverse health event if necessary.

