## 9. Sample size

The primary outcome for this trial will be the number of unprotected sex acts (vaginal, oral, and anal). In the RESPECT feasibility trial (), we observed an excess of zeroes in this outcome at baseline - from both people who always used protection, and those who had not engaged in any acts at all. Therefore, to calculate the sample size we followed the method outlined for a zero-inflated Poisson analysis by Wang & Fan (). In the feasibility trial, at baseline, participants had undertaken an average of 9 unprotected sex acts in the previous three months. Extrapolating this across 12 months, we might expect to observe an average of approximately 40 unprotected sex acts a year in the control group. Assuming a 0.35 zero-inflated probability in both groups, we would have 90% power, with a 5% two-sided significance, to detect a 25% reduction in the intervention group in the number of unprotected sex acts (40 to 30 acts) over a 12-month period, with 296 participants. Inflating for 20% attrition, we would require 370 participants to be randomised. To

allow for some flexibility in the parameters, as they are based on the feasibility trial, we shall aim to recruit 400 participants.

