11.1 Sexual Health Intervention

University for the Common Good

The sexual health intervention was designed and developed during the RESPECT feasibility study (18). It comprises of three components:

- 1) Raising awareness of issues related to sexual health such as contraception choices, how to engage in sex acts safely, positive intimate relationships (Information)
- 2) Facilitating dialogue and reflection on own (and sexual partners) sexual health and unmet needs for advice, treatment, testing, contraception, skills (Motivation)
- 3) Behavioural skills (such as how to use a condom correctly), negotiate safer sex and/or communicate preferences or boundaries effectively (Behaviour)

The intervention manual is divided into sections on a variety of topics and includes interactive exercises rather than didactic presentation of information. There is flexibility to focus on people's specific needs and interests, sexuality and gender identity.

*Timing:* It will be delivered over 3 x one-hour 1:1 sessions by a person from the local NHS service (interventionist) who has received specific training from the study team. The three intervention sessions should be delivered as soon as practical after randomisation but must be completed before the 3-month follow-up data collection time point.

Location: It is designed to be delivered face to face or using remote videoconferencing sessions. In the feasibility study it was delivered in a person's home or using an office in a local service, and this was found to be acceptable to participants. The intervention can also be delivered on inpatient mental health units if a patient is awaiting discharge but remain in inpatient care due to the unavailability of suitable community placement.

Interventionist: An Intervention lead will work with the NHS sites to provide training and supervision for those who will be delivering the intervention. The criteria for the interventionists are broad:

- · Experience of working with people who live with SMI
- Comfortable talking about sexual health and sexual practices
- Ability to work in a non-judgemental way, using core skills of engagement, empathy, listening, reflecting and summarising. Each recruiting site will be required to provide interventionists with protected time to deliver the intervention to participants in the NHS organisation (3 x one-hour sessions per participant).

The person does not require prior expertise of working in sexual health.

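### The primary model makes no allowance for clustering by interventionist, which exists in one arm only; a pre-specified sensitivity analysis would cover it

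*Protocol*

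**What the plan says.** Section 18.1 compares the arms with a zero-inflated Poisson regression and states: "The model will be adjusted for relevant baseline covariates as well as site as a random effect". If assumptions fail or there is overdispersion, "other appropriate models will be considered, such as a negative binomial regression model". Interventionists are not mentioned in that section.

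Under section 11.1 each intervention participant is offered three one-hour individual sessions with a trained member of local NHS staff, who needs no background in sexual health. Under section 11.2 controls have no such contact. On the pairing, section 8.4 says: "The intervention coordinator/lead will assign an interventionist to the participant and will confirm to YTU who this is". The role table in section 1.3 repeats that the pairings are confirmed to the trials unit.

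Section 9 gives the power: "we would have 90% power, with a 5% two-sided significance, to detect a 25% reduction in the intervention group" ("40 to 30 acts) over a 12-month period, with 296 participants"). It assumes a zero-inflation probability of 0.35 in both arms, inflates 296 to 370 for 20% attrition, and sets the target at 400 to leave room for uncertain parameters. It does not mention clustering.

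**The concern.** Participants seen by the same interventionist share that person's skill and style. If interventionists differ in effect, outcomes in the intervention arm are correlated within interventionist, while controls remain independent. A site intercept moves both arms of a site up or down together, so it cannot represent variation found in one arm only. With a single interventionist at a site, that variation acts as a site-by-treatment effect, which the stated model lacks. A negative binomial model allows for extra spread between participants, but still treats two participants of one interventionist as independent.

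At stake are the standard error and coverage of the primary rate ratio and, to a lesser degree, the power claimed in section 9.

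**Working it through.** **Inputs from the protocol.** Zero-inflation probability p = 0.35; means of 40 and 30 acts (ratio 0.75); two-sided 5% level; 90% power; 296 analysed, 370 after 20% attrition; target 400 (section 9). Allocation is 1:1 (section 8.4). Twelve localities recruit at a time (section 6.2).

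**Assumed, not in the protocol.** ICC of 0.01 to 0.10. Two interventionists per locality, so 24 in all. With 400 × 0.8 = 320 analysed, or 160 per arm, that is 160/24 ≈ 6.7 analysed participants per interventionist. One per locality gives 160/12 ≈ 13.3.

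**Reproducing 296.** For the log ratio of means under a zero-inflated Poisson, the variance per participant is (1 + pλ)/((1 − p)λ).

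- Control: (1 + 0.35 × 40)/(0.65 × 40) = 15/26 = 0.5769
- Intervention: (1 + 0.35 × 30)/(0.65 × 30) = 11.5/19.5 = 0.5897
- n per arm = (1.960 + 1.282)² × (0.5769 + 0.5897)/(ln 0.75)² = 10.507 × 1.1667/0.08276 = 148.1

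Twice 148 is 296, and 296/0.8 = 370. The plan's figures reproduce with no design effect, so the 90% assumes no interventionist clustering. At 160 per arm the same formula gives 92.1%.

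**Adding clustering in one arm.** The design effect DE = 1 + (m − 1) × ICC multiplies the intervention variance only.

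- Power with n per arm = Φ(0.2877/√[(0.5769 + 0.5897 × DE)/n] − 1.96)
- Type I error if clustering is ignored = 2 × [1 − Φ(1.96/√((1 + DE)/2))], with equal arm variances under the null and interventionist effects varying around zero

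With m = 6.7:

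| ICC | DE | Type I error | Power, 296 analysed | Power, 320 analysed |
|---|---|---|---|---|
| 0 | 1.000 | 5.0% | 90.0% | 92.1% |
| 0.01 | 1.057 | 5.3% | 89.1% | 91.3% |
| 0.03 | 1.171 | 6.0% | 87.5% | 89.8% |
| 0.05 | 1.285 | 6.7% | 85.8% | 88.3% |
| 0.10 | 1.570 | 8.4% | 81.5% | 84.3% |

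One line in full, for ICC 0.03 at 320 analysed: the summed variance is 0.5769 + 0.5897 × 1.171 = 1.2675; the standard error is √(1.2675/160) = 0.0890; 0.2877/0.0890 − 1.96 = 1.27; Φ(1.27) ≈ 0.898.

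At ICC 0.05 the true standard error is √(1.3347/1.1667) = 1.07 times the model's, so a nominal 95% interval covers about 93.3%.

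**Sensitivity to cluster size.** With m = 13.3 and ICC 0.05, type I error is 8.7% and power at 320 analysed is 83.7%. With m = 13.3 and ICC 0.01 they are 5.7% and 90.5%.

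**Does site adjustment absorb it?** A simulation with a continuous outcome, 12 sites of 13 participants per arm, site adjusted as fixed effects and 1,500 runs per setting gave these type I errors:

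| ICC | One interventionist per site | Two per site |
|---|---|---|
| 0 | 4.2% | 5.4% |
| 0.05 | 7.7% | 7.1% |
| 0.10 | 11.9% | 7.7% |

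The simulation error is about √(0.05 × 0.95/1500) ≈ 0.6 percentage points. Site adjustment does not remove the effect. The simulation uses a continuous analogue, not the zero-inflated model itself.

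**The case against.** Section 18 defers to a detailed SAP, which is not at hand. Provider effects are often handled there. Section 18.1 does not say that site is the only random effect, and its fallback for failed assumptions is broad enough to admit another term. This stands in part: nothing prevents the SAP from adding one. But the protocol does name the random effect and does size the trial on independence, and its one example of a fallback model does not deal with clustering.

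Nothing in the protocol shows that interventionists differ. The manual, common training, monthly supervision and session checklists (sections 11.1 and 11.2's preceding text on fidelity and training) are meant to limit variation, and a refreshed pool of staff could make clusters small. This stands, and the point must remain conditional.

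The upper end of the ICC range is demanding. At ICC 0.10 the between-interventionist SD is √(0.10 × 0.5897) = 0.24 on the log scale, against an effect of 0.29. About Φ(−0.288/0.243) ≈ 12% of interventionists would then increase unprotected acts.

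A reader might infer that type I error is inflated whatever the truth. It is not. If the intervention does nothing in anyone's hands, interventionists add no variance. Inflation needs some who help and some who harm, averaging to zero.

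A reader might also infer that the term belongs in the primary model. With few clusters and a second random effect in a zero-inflated model, convergence and small-sample problems are real, so that is a matter of preference.

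**Conclusion.** The point holds as a conditional one. If interventionists differ in effect, the model as described gives a primary confidence interval that is somewhat too narrow, and neither the site effect nor the count-model fallback corrects it.

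The size cannot be settled from the protocol. With two interventionists in each of 12 localities and an ICC of 0.05, the standard error is understated by about 7% and power at the recruitment target is about 88%.

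It would be tempting to conclude that the trial is underpowered on this account. The protocol does not support that. The target of 400 gives 92% without clustering, and with 6.7 analysed per interventionist it keeps power at about 90% up to an ICC of about 0.03. The margin runs out only with a larger ICC or fewer interventionists. The same margin is also meant to cover the other uncertain parameters in section 9.

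**What to change.** Add to section 18.1 (and carry into the SAP) a pre-specified sensitivity analysis of the primary outcome with a random effect for interventionist in the intervention arm only, using the pairings already sent to the trials unit. Keep participants who attend no session under their assigned interventionist, or treat them as singletons if none was assigned. Report the estimated interventionist variance next to the rate ratio.

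State in section 9 that the 90% power assumes no interventionist clustering.

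The cost is wording, because the identifier is already collected. The downside is a slightly wider interval in that analysis and possible work to make the model converge.

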## 18.2 Secondary analysis

The secondary outcomes will be analysed using appropriate regression models, adjusted in the same way as the primary analysis, but including a random effect for participant to account for the repeated measures. HIV-KQ, Condom use Self-Efficacy Scale, and Behavioural Intentions for Safer Sex are continuous outcomes, and a mixed-effects linear regression model will be used. As there is no scoring for the 4-item Motivation to Engage in Safer Sex measure, the responses to each question will be compared between the two groups using a multinomial logistical regression.

moreRESPECT\_Protocol

IRAS ID: 309345

REC Reference: 23/NW/0157

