## 10.2 Secondary outcomes

Includes a set of questionnaires that assess knowledge, motivation and behavioural intention to adopt safer sexual behaviour will be used and captured through participant CRFs at baseline and follow-up. These have been developed by Carey et al (2004) () and used in trials of sexual health promotion for people with SMI as well as in the RESPECT study ():

Knowledge about human immunodeficiency virus and sexually transmitted infections –
HIV- Knowledge Questionnaire (HIV-KQ) (): a 17-item measure that assesses
knowledge about HIV. This originally comprised 18 items but we removed one question
about lamb-skin condoms as this is now outdated.

moreRESPECT\_Protocol

IRAS ID: 309345

REC Reference: 23/NW/0157

- Motivation to Engage in Safer Sex (): a four-item scale to assess people's own
  perception of their risk of infection with a STI.
- Condom use Self-Efficacy Scale (): an 18-item Likert scale to assess attitudes towards
  the use of condoms as well as questions on self-efficacy in the use and negotiation of use.
- Behavioural Intentions for Safer Sex (): an eight-item measure in which patients are presented with a scenario describing a possible sexual encounter and asked to rate how likely it was that they would engage in six risky or protective behaviours (e.g. 'I will tell the person I don't want to have sex without a condom'). Patients respond to each behaviour using a six-point scale (ranging from 0 'definitely will not do' to 5 'definitely will do'.
- General questions about sexual health: items adapted from the National Survey of Sexual Attitudes and Lifestyle (NATSAL)
- Quality of life EQ-5D-5L: standardised instrument for use as a measure of health outcome that is applicable to a wide range of health conditions and treatments ().
- Recovering Quality of Life (ReQoL): 20-item patient-reported outcome measure that has been developed to assess the quality of life for people with different mental health conditions ()
- Health care resource use: a bespoke resource use questionnaire will be used to capture
  all health care use, including medications.

Demographics and other relevant information will also be collected in the baseline CRFs: age, SMI diagnosis, sexual health history, non-volitional sex, relationship status, socio-economic data, gender identity, sexual identity, ethnicity.

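### Lack of a total score justifies analysing the four motivation items separately, but not treating their answers as unordered; if the answers are ordered, multinomial regression loses power and gives no single effect per item

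*Protocol*

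**What the plan says.** Section 10.2 of the protocol lists Motivation to Engage in Safer Sex as a secondary outcome and describes it as "a four-item scale to assess people's own" "perception of their risk of infection with a STI". It does not say how many answer options each item has, how they are worded, or whether they are graded.

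Section 18.2 sets the analysis. Its premise is "As there is no scoring for the 4-item Motivation to Engage in Safer Sex measure", and its conclusion is that the answers to each item will be "compared between the two groups using a multinomial logistical regression". Secondary outcomes are adjusted as in the primary analysis (baseline covariates and a site random effect, Section 18.1), "including a random effect for participant to account for the repeated measures". For testing, Section 18 states: "The analyses will be conducted at a 5% significance level using two-sided statistical tests, unless otherwise specified".

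No power, effect size or summary measure is given for this outcome. Motivation is named in objective 3 (Section 5.2).

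**The concern.** The stated reason does not lead to the stated method. Without a total score, the four items cannot be added up, so each must be analysed separately. Whether the answers within an item are ordered is a different question, and Section 18.2 does not address it.

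A multinomial model ignores any order. It compares each answer category with a reference category and estimates a separate treatment odds ratio for each comparison. If the answers run from, say, low to high perceived risk, a general move in one direction is split over several odds ratios, and a joint test spends several degrees of freedom on what is essentially one shift. The reader of the results then has no single statement of the treatment effect on an item, and a real shift is more likely to be missed.

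**Working it through.** **Inputs from the protocol.** Four items, each analysed by multinomial regression (18.2); two-sided 5% level (18); 1:1 allocation (8.4); target of 400 with 20% attrition (9), so 400 × 0.8 = 320 evaluable.

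**Inputs that must be assumed.** The number of options K (3 to 7 examined), that they are ordered, that the treatment effect is a proportional-odds shift, that the multinomial comparison is a joint test on K−1 degrees of freedom, and a benchmark power for the ordinal test (80% or 90%). None of these is in the protocol.

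**The plan's own figure.** There is none for this outcome. The sample size in Section 9 concerns the primary outcome only. It can be reproduced (148.1 per arm, about 296 in total, and 296/0.8 = 370) and is not in question.

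**Step 1: number of treatment effects.** Each item gives K−1 odds ratios, so four items give 4(K−1): 4 × 2 = 8, 4 × 3 = 12 and 4 × 4 = 16 for K = 3, 4 and 5. An ordinal model gives 4 × 1 = 4.

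**Step 2: power.** A one-degree-of-freedom test with benchmark power has noncentrality (z for 5% two-sided + z for power)². This is (1.960 + 0.842)² = 7.85 for 80% and (1.960 + 1.282)² = 10.51 for 90%. The multinomial power is the probability that a noncentral chi-square with K−1 degrees of freedom and that noncentrality exceeds the 5% critical value.

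| Options K | Degrees of freedom | Power when ordinal test has 80% | Loss (points) | Power when ordinal test has 90% | Loss (points) |
|---|---|---|---|---|---|
| 3 | 2 | 70.9% | 9.1 | 83.5% | 6.5 |
| 4 | 3 | 64.5% | 15.5 | 78.4% | 11.6 |
| 5 | 4 | 59.5% | 20.5 | 74.0% | 16.0 |
| 6 | 5 | 55.5% | 24.5 | 70.3% | 19.7 |
| 7 | 6 | 52.1% | 27.9 | 67.0% | 23.0 |

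**Step 3: check by simulation.** 10,000 trials per setting were simulated with 320 participants, one time point, no covariates and a proportional-odds shift. A multinomial likelihood-ratio test was compared with a rank test, which is the score test of the ordinal model. For K = 3, 4 and 5 the losses were 9.4, 14.7–15.1 and 19.6–20.1 points at 80%, and 6.6, 11.3–11.7 and 15.7–16.8 points at 90%. The ranges cover even and skewed answer distributions. The 80% benchmark corresponded to an odds ratio of about 1.74 to 1.78.

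**Step 4: where the loss disappears or reverses.** With two options the multinomial model is ordinary logistic regression: one odds ratio and no loss. With a non-monotone effect the ordering can hurt. For four options at 25/25/25/25% in one arm and 33/17/17/33% in the other, with 320 participants, the multinomial test had 68% power and the rank test 5%.

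**The case against.** The best reply is that the premise is not in the document. Section 10.2 states the answer format for neighbouring measures (a Likert format for condom self-efficacy, a six-point range for behavioural intentions) but not for this one, and calling it a scale need not describe how each item is answered. The trial team holds the instrument. Its options may be unordered, or may include a category such as 'don't know' that breaks the order. A multinomial model is also valid for ordered answers, and it avoids the proportional-odds assumption. This is one secondary outcome with no power claim, and much analysis detail properly belongs in the SAP.

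Most of this stands. It makes the point conditional and keeps it small. It does not rescue the reasoning in Section 18.2: the protocol itself names the model and gives a reason, and that reason does not bear on order. The general promise in Section 18 to check assumptions would not correct it either, because a multinomial model makes no ordering assumption that could fail.

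Three stronger readings are tempting but unsupported:

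- **A fixed power loss of about 9 to 20 points.** This needs 3 to 5 ordered options, an 80% benchmark and a proportional-odds shift. The protocol gives none of these.
- **64 odds ratios against 16.** With five options and separate effects at each of the four follow-ups, 16 × 4 = 64 and 4 × 4 = 16. Section 18.2 does not say that effects will be estimated separately at each time point.
- **The model will not converge.** The random effects add complexity, but category-specific random effects are one way to fit the model, not a stated requirement. No fit was attempted, so nothing can be said about convergence.

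**Conclusion.** The point holds in conditional form. The reason in Section 18.2 supports item-by-item analysis and no more. If an item has three or more ordered options, the planned model replaces one odds ratio with K−1. For a proportional-odds shift it also gives up power: from about 6.5 points (three options, 90% benchmark) to about 28 points (seven options, 80% benchmark). With two options the loss is nil, and for a non-monotone effect the planned model can have the advantage.

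That the answers are ordered is inferred from the description in Section 10.2 and is not confirmed. The power figures come from an unadjusted comparison at one time point, so they show the relative cost of the extra degrees of freedom and do not forecast this trial's power.

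No bias or invalid test is shown, and the primary analysis and sample size are unaffected. This is a low-priority improvement in efficiency and interpretability for one secondary outcome.

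**What to change.** In Section 10.2, state the answer options of the four items. In Section 18.2, specify for items with ordered answers a mixed-effects ordinal (proportional odds) logistic regression with the same covariates and random effects as the other secondary analyses, reporting one odds ratio per item with its 95% confidence interval. Keep multinomial regression for items with unordered answers. Where proportional odds clearly fails, use partial proportional odds or multinomial regression.

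The cost is a sentence or two of text, with no change to data collection or sample size. The drawback is reliance on the proportional odds assumption. It can be checked, and the fallback covers a clear failure, but an effect that moves answers towards both ends would be poorly summarised by one odds ratio.
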